## 6. MILESTONES

Milestone	Planned date	
Completion of feasibility assessment	29 February 2024 (completed)	
Draft protocol submission to the FDA	30 April 2024 (completed)	
Final protocol submission to the FDA	16 August 2024 (completed)	
Registration in the HMA-EMA Catalogue of RWD studies	16 August 2024	
	EU PAS number: EUPAS1000000267	
Start of data collection*	19 August 2024	
End of data collection	15 September 2025	
Interim report 1**	20 December 2024 (completed)	
(2023/2024 RSV season SCRI and descriptive analysis)		
Interim report 2	21 February 2025 (completed)	
(2024/2025 RSV season 1st RCA report)		
Interim report 3	08 August 2025	
(2024/2025 RSV season 2 nd RCA report)		
Final study report to the FDA	30 January 2026	
(2023/2024 RSV season SCRI and descriptive analysis; 2024/2025 RSV season SCRI and descriptive analysis; combined 2 seasons SCRI and descriptive analysis)		

\* Start of data collection will occur after submission of final protocol and SAP finalization, which may be adjusted should there be any further feedback from the FDA.

Abbreviations: HMA-EMA, Heads of Medicines Agencies – European Medicines Agency; RWD, Real-World Data.

\*\* Timeline for the 1st interim report may be adjusted should there be any significant delay in start of data collection

### 7. RATIONALE AND BACKGROUND

Respiratory syncytial virus (RSV) is a common, contagious virus that causes mild, cold-like symptoms, but may cause severe disease with a need for hospitalization in infants and older adults.(1) RSV infection in older adults can result in Lower Respiratory Tract Disease (LRTD), which can lead to serious, life-threatening pneumonia and bronchiolitis. According to the Centers for Disease Control and Prevention (CDC), RSV infection causes approximately 60,000 - 120,000 hospitalizations and 6,000 - 10,000 deaths annually among adults ages 65 years of age and older.(1) The U.S. FDA approved RSVpreF (ABRYSVO) RSV vaccine on 31 May 2023 for individuals 60 years of age and older to prevent severe RSV and on 21 August 2023 for pregnant individuals at 32 through 36 weeks gestational age to protect newborns through passive immunity. (2, 3) On 22 October 2024, the vaccine was approved for individuals 18 through 59 years of age who are at increased risk for LRTD.(4) The CDC initially recommended that adults aged 60 years and older receive RSV vaccination using shared clinical decision-making.(5) Following the Advisory Committee on Immunization Practices (ACIP) meeting, the CDC further recommended on 26 June 2024 that all adults aged 75 years and older, and adults aged 60-74 years who are at increased risk for severe RSV disease, should receive the vaccine. (6, 7)

GBS is a rare, serious acute demyelinating disease, where damage to the nerve causes muscle weakness and sometimes paralysis.(8) Although the cause of GBS is not fully understood, the syndrome often follows infection with a virus or bacteria; furthermore, it has been found that there is an increased risk for GBS following vaccine administration, an association that was first observed after the 1976 swine flu vaccinations.(8, 9) GBS is a rare, serious acute demyelinating disease, where damage to the nerve causes muscle weakness and sometimes paralysis.(8) Although the cause of GBS is not fully understood, the syndrome often follows infection with a virus or bacteria; furthermore, it has been found that there is an increased risk for GBS following vaccine administration, an association that was first observed after the 1976 swine flu vaccinations.(8, 9)

Across all RSVpreF clinical trials, inflammatory neurologic events were reported in 3 of 20,255 adults aged ≥60 years within 42-days after vaccination with RSVpreF (1 case of GBS, 1 case of Miller Fisher syndrome [a variant of GBS] and 1 case reported as undifferentiated motor-sensory axonal polyneuropathy).(10) GBS is an important potential risk, which is mentioned in the ABRYSVO Risk Management Plan.(7) Pfizer has an ongoing Postmarketing Requirement (PMR) PASS (protocol # C3671031), that is planned over multiple RSV seasons to evaluate any small or modest risk of GBS (e.g., 2-fold) following ABRYSVO vaccination using the fully adjudicated CMS Medicare claims. The study's first interim report will be available in December 2026 and the final report in May 2030. On 09 November 2023, FDA informed Pfizer of a few potential cases of GBS among older adults receiving ABRYSVO that were reported to the FDA's Vaccine Adverse Event Reporting System (VAERS), highlighting a need to rapidly assess the risk of GBS following ABRYSVO administration.(11)

The proposed post-marketing safety study will provide a timely, targeted assessment of GBS after ABRYSVO vaccination during the initial vaccine uptake period of two consecutive RSV seasons, 2023/2024 and 2024/2025, that will address the gaps in safety evidence from

prelicensure trials and early passive adverse event reporting. The study will encompass two analytical approaches: a signal detection (RCA) and a comparative (SCRI) approach.

RCA is an established method of near real-time surveillance that periodically assesses data for safety signal as exposures accrue by comparing observed incidence rates of GBS to an expected background rate. To detect an early safety signal for GBS, Pfizer proposes to conduct a near real-time surveillance of risk of GBS following ABRYSVO among older adults in the U.S.

The SCRI study design is a commonly used method in vaccine safety studies, to evaluate the association between a transient exposure, such as vaccination, and an acute event, such as an adverse reaction. (12) This approach inherently controls for time-invariant confounders within an individual, such as genetic factors, chronic health conditions, as well as long-term lifestyle socio-economic status. To evaluate the risk of GBS following ABRYSVO, Pfizer proposes to conduct an SCRI analysis among older adults in the U.S.

The complementary approaches of conducting an active surveillance study using an RCA for signal detection, and a comparative SCRI analysis to further assess the risk for an adverse event following vaccination is essential for a robust vaccine safety study. It combines the advantage of timely signal detection and the ability to perform an in-depth analysis that is hypothesis-driven and well-controlled for time-invariant confounders. The approach ultimately ensures a robust measurement of the safety of vaccines in the indicated population.

This non-interventional study is designated as a PASS and is a post-marketing commitment to the FDA.

## 8. RESEARCH QUESTION AND OBJECTIVES

Research question: What is the incidence rate of GBS following vaccination with ABRYSVO among older adults aged 65 years of age or older enrolled in CMS Medicare databases and individuals aged 60-64 years enrolled in the IQVIA PharMetrics Plus claims database (PharMetrics Plus database) as compared to the expected incidence rate of GBS in a comparable population?

The research objectives are:

- To conduct near real-time monitoring of the incidence of GBS following vaccination with ABRYSVO among individuals aged 65 years of age or older enrolled in CMS Medicare databases using RCA study design; and
- To assess if there is an elevated risk of GBS following vaccination with ABRYSVO among individuals aged 65 years of age or older enrolled in CMS Medicare databases, using SCRI study design; and
- To descriptively monitor the incidence of GBS following vaccination with ABRYSVO in individuals aged 60-64 years enrolled in PharMetrics Plus database.

#### 9. RESEARCH METHODS

## 9.1. Study Design

This will be a non-interventional cohort study among older adults enrolled in CMS Medicare databases and PharMetrics Plus database (Section 9.4). The surveillance period for RSV vaccinations (i.e., the indexing period) will span 2 RSV seasons (i.e., 2023/2024 and 2024/2025 seasons), beginning on ABRYSVO's approval on 31 May 2023. Two RSV seasons are included to increase sample size and rapidly assess a modest to high risk (3- to 5-fold) of GBS after ABRYSVO vaccination while a separate, long-term PMR PASS (protocol # C3671031) spanning 4.5 RSV seasons or more is being conducted to detect any small risk of GBS (e.g., 2-fold) following ABRYSVO vaccination using the fully adjudicated claims in CMS Medicare. There will be descriptive monitoring of GBS incidence following ABRYSVO vaccination among adults aged 60-64 years of age.

The baseline period for an individual will be defined as 365 days prior to the date of the ABRYSVO administration (i.e., the index date), to assess the individual's demographic and clinical characteristics, and to rule out prevalent GBS cases. Two complementary approaches will be used to address the study objectives and evaluate the risk of GBS among individuals who receive ABRYSVO: RCA and SCRI. A patient-level case-centered analysis will also be conducted to better understand the severity and risk factors associated with all GBS cases identified in the analytic populations from two databases: CMS Medicare administrative databases and PharMetrics Plus database. The CMS Medicare database covers individuals aged 65 and older, while PharMetrics Plus data will cover individuals aged 60-64 years. Together, these two data sources will provide age representation for the currently approved indication for ABRYSVO for older adults. Given the more limited age range for commercially insured adults 60-64 years, analyses for this age group will be primarily descriptive based on available sample size.

## 9.1.1. The Study Design of RCA Methodology

For signal detection, an RCA will be conducted during the 2024/2025 RSV season, built upon cumulative data from the 2023/2024 RSV season, by periodically evaluating the near real-time incidence of GBS following vaccination as the data become available on a monthly basis. The observed number of GBS cases in the ABRYSVO-vaccinated population will be compared to an expected number of GBS cases based on an estimated background rate of GBS from a comparable population (Section 9.7.3.1). A group sequential testing approach will be used for repeated testing of continuously accumulating data to minimize false positive signals. The detailed study design and study periods of the RCA analysis are described in Section 9.1.1.1. The background rate of GBS will be estimated from individuals who received seasonal influenza vaccines using historical data across the 2022 and 2023 influenza seasons. The historical influenza-vaccinated population is expected to be more similar to ABRYSVO-vaccinated individuals in terms of demographics, clinical characteristics, and

<sup>9 The RCA is a hypothesis-testing standard signal detection study with parameters in line with established rule-out risks. In our study, it is set up to provide early safety signals but will not be used to determine association between the exposure and outcome.

health-seeking behavior (Section 9.7.3.1). The RCA will allow timely safety signal detection of GBS risk following vaccination with ABRYSVO.

The indexing period for the RCA will be from 31 May 2023 (e.g., first date of ABRYSVO vaccination) to 10 January 2025 (e.g., last date of ABRYSVO vaccination). For the RCA, a primary risk interval of 1-21 days following the index date will be evaluated to allow sufficient time for data completion and to prioritize more timely analysis during the season. Currently, >90% GBS events that occurred after RSV vaccinations were within 21 days of vaccination.(13) A secondary risk interval of 1 – 42 days after the index date will also be assessed in the RCA.

The overall RCA study period will span the baseline period, indexing period, and follow-up period, i.e., from 31 May 2022 to 21 February 2025.

[figure not shown]
## 9.1.1.1. The Study Periods of RCA Methodology

The RCA analysis will be launched in the 2024/2025 RSV season, with cumulative data from the 2023/2024 RSV season. An early vaccination cutoff will be used in the RCA to balance the timeliness of in-season surveillance and the more complete capture of data to enhance results validity. The key study periods of the RCA analysis are described below:

- **Study Period:** 31 May 2022 21 February 2025
- Indexing period (e.g., vaccination period): 31 May 2023 10 January 2025
- Index Date: The date of ABRYSVO administration
- **Baseline period:** 365 days prior to the index date
- Follow-up period:
  - **Post-vaccination risk interval:** 1-21 and 1-42 days after the index date as the primary and secondary risk interval, respectively.

Figure 1 shows the study design and study period of the RCA analysis.

Figure 1. Study design and key study periods of the rapid cycle analysis

Abbreviations: Dx, diagnosis; GBS, Guillain-Barre Syndrome.

Figure 2 shows the study periods of the monthly RCA analysis.

Figure 2. The study periods of rapid cycle analysis during the 2023/2024 and 2024/2025 RSV seasons

Abbreviations: GBS, Guillain-Barre Syndrome; RCA, rapid cycle analysis.

Note: The data maturation period allows for claims in the CMS Medicare FFS administrative database to be completed in the system. Historically, approximately 90% of IP and OP claims are submitted to the CMS within 2 months after service date. (14, 15)

Note: The population for the RCA #1 was included in Interim report 2; the results of the RCA will be included in Interim report 3.

## 9.1.2. The Study Design of SCRI Methodology

In addition, as a comparative analysis, SCRI analyses will be conducted for the 2023/2024 and 2024/2025 RSV seasons, both separately and as a pooled analysis, to provide more conclusive evidence for the association between vaccination and GBS. The SCRI will assess the risk of GBS following ABRYSVO vaccination by comparing the incidence rate of GBS during the pre-specified post-vaccination

control interval within the vaccinated individuals. The SCRI design effectively controls for time-invariant confounding. The detailed study design and study periods of the SCRI analysis are described in Section 9.1.2.1. A final pooled analysis using individual-level data from 2 RSV seasons (2023/2024 and 2024/2025) will be conducted which will allow for a more comprehensive and accurate assessment of the association between ABRYSVO and GBS with a larger sample size. The comparative SCRI analysis will assess the risk of GBS following vaccination as an in-depth analysis that is hypothesis-driven and well-controlled for time-invariant confounders.

The indexing period for the 2023/2024 RSV season SCRI analysis will be from 31 May 2023, starting from the date of ABRYSVO's approval, to 29 February 2024. The indexing period for the 2024/2025 RSV season SCRI analysis will be from 31 May 2024 to 28 February 2025. An early vaccination cutoff in February will be used as preliminary count data from the CMS for the 2023/2024 season indicate that ABRYSVO vaccinations peaked in October, and >90% of RSV vaccinations for the season are expected to have been administered by the end of February; this is also consistent with historical data for other seasonal vaccines such as influenza vaccines where >95% vaccinations of the season were administered by the end of February. (16, 17) Furthermore, the February end date allows sufficient time for completion of the claims in the CMS Medicare database before analysis begins (e.g., >90% IP and OP claim completeness within 2 months after service date). Previous studies have also shown that an early cutoff of the indexing period when assessing risk of GBS following influenza vaccination did not impact the results.(18) The indexing period for the combined two season analysis will be from 31 May 2023 following ABRYSVO's approval to 28 February 2025. The follow-up period for the SCRI analysis will consist of the post-vaccination risk interval of the individuals received ABRYSVO, defined as 1-21 and 1-42 days after the index date, as the primary and secondary risk intervals, respectively. These windows are consistent with the onset of GBS cases during the ABRYSVO clinical studies and also with previous vaccine safety studies that have evaluated the risk of GBS.(8, 12, 18, 19) The follow-up will also include the post-vaccination control interval, defined as 43-84 days after the index date. The total follow-up period of each patient will be 84 days for the SCRI analysis.

The overall SCRI study period will span the baseline period, indexing period, and follow-up period, i.e., from 31 May 2022 to 23 May 2025.

## 9.1.2.1. The Study Periods of SCRI Methodology

[figure not shown]
The SCRI analysis spans the 2023/2024 and 2024/2025 RSV seasons, and the follow-up period consists of the pre-specified post-vaccination risk and control intervals. The key study periods of the SCRI analysis are described below:

- Study Periods:
  - o **2023/2024 Study Period:** 31 May 2022 23 May 2024
    - **Indexing period:** 31 May 2023 29 February 2024

- o **2024/2025 Study Period:** 31 May 2023 23 May 2025
  - Indexing period: 31 May 2024 28 February 2025
- o Combined two season study period: 31 May 2022 23 May 2025
  - **Indexing period:** 31 May 2023 28 February 2025
- Note: As detailed in Section 9.1.2, the indexing period will end in February as >90% of RSV vaccinations are anticipated to be administered by that time, as a trade-off to balance timely analyses and more complete data capture.
- Index Date: The date of ABRYSVO administration
- **Baseline period:** 365 days prior to the index date
- Follow-up period:
  - Post-vaccination risk period: 1-21 and 1-42 days after the index date as the primary and secondary risk interval, respectively. Days 22-42 after the primary 1-21 days risk interval will be considered a washout period and will not be included in the analyses to avoid any carryover effects.
  - o **Post-vaccination control period:** 43-84 days after the index date

Figure 3 shows the study design and key study periods of the SCRI analysis.

[figure not shown]
Figure 3. Study design of the self-controlled risk interval analysis

Abbreviations: Dx, diagnosis; GBS, Guillain-Barre syndrome; RSV, Respiratory Syncytial Virus.

Figure 4 shows the study period of SCRI analysis in relation to the RSV seasons.

Figure 4. The study period of self-controlled risk interval analysis during 2023/2024 and 2024/2025 RSV seasons

Abbreviations: GBS, Guillain-Barre Syndrome; RSV, respiratory syncytial virus; SCRI, self-controlled risk interval.

Note: The data maturation period allows for claims in the CMS Medicare FFS administrative database to be completed in the system. Historically, approximately 90% of Medicare IP and OP claims were submitted to the CMS within 2 months after service date. (14, 15)

## 9.1.3. The Descriptive Analysis of Individuals Aged 60-64 Years Enrolled in PharMetrics Plus Database

Given the more limited age range for commercially insured adults 60-64 years, analyses for this age group will be primarily descriptive based on available sample size. The inferential analysis, SCRI, may be considered contingent on sample size.

For the descriptive analyses of GBS incidence following vaccination with ABRYSVO in individuals aged 60-64 years enrolled in PharMetrics Plus database, the indexing period of the 2023/2024 RSV period for evaluating exposure to ABRYSVO will be from 31 May 2023 to 29 February 2024. For the 2024/2025 RSV season, the indexing period will be from 31 May 2024 to 28 February 2025. For the combined RSV season analysis, the indexing period will be from 31 May 2023 to 28 February 2025.

The overall study period will span the baseline period, indexing period, and follow-up period, i.e., from 31 May 2022 to 11 April 2025. The detailed study design and study periods of the SCRI analysis are described in Section 9.1.3.1.

# 9.1.3.1. The Study Periods of Descriptive Analysis of Individuals Aged 60-64 Years Enrolled in PharMetrics Plus Database

[figure not shown]
The descriptive analysis spans the 2023/2024 and 2024/2025 RSV seasons, and the follow-up period consists of the pre-specified post-vaccination risk intervals. The key study periods of the descriptive analysis are described below:

## • Study Periods:

- o **2023/2024 Study Period:** 31 May 2022 11 April 2024
  - Indexing period: 31 May 2023 29 February 2024
- 2024/2025 Study Period: 31 May 2023 11 April 2025
  - **Indexing period:** 31 May 2024 28 February 2025
- o Combined two season study period: 31 May 2022 11 April 2025
  - Indexing period: 31 May 2023 28 February 2025
- **Index Date:** The date of ABRYSVO administration
- **Baseline period:** 365 days prior to the index date
- Follow-up period:
  - O **Post-vaccination risk period:** 1-21 and 1-42 days after the index date as the primary and secondary risk interval, respectively.

Figure 5 shows the study design and key study periods of the descriptive analysis.

Figure 5. Study design of the descriptive analysis of individuals aged 60-64 years

Abbreviations: Dx, diagnosis; GBS, Guillain-Barre syndrome; RSV, Respiratory Syncytial Virus.

Figure 6 shows the study period of the descriptive analysis of individuals aged 60-64 years in relation to the RSV seasons.

Figure 6. The study period of the descriptive analysis of individuals aged 60-64 years during 2023/2024 and 2024/2025 RSV seasons

The study period of the descriptive analysis of individuals aged

60-64 years **Indexing Period** 42-day Follow-up Period End of the End of the End of 7 days to Start of the Complete Start of the study indexing period study period capture GBS data maturation indexing period period 2023/2024 season analysis 31 May 2022 31 May 2023 29 Feb 2024 11 Apr 2024 18 Apr 2024 01 Sept 2024 2024/2025 season analysis 31 May 2023 31 May 2024 28 Feb 2025 11 Apr 2025 18 Apr 2025 01 Oct 2025 Analysis of both seasons 31 May 2022 31 May 2023 28 Feb 2025 11 Apr 2025 18 Apr 2025 01 Oct 2025

Abbreviations: GBS, Guillain-Barre syndrome; RSV, Respiratory Syncytial Virus.

Note: The PharMetrics Plus database contains fully-adjudicated claims with a data lag of approximately six months. (20) The indexing period for the descriptive analysis has accounted for the lag.

[figure not shown]

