Milestones: The feasibility assessment was completed on 29 February 2024. The draft protocol will be submitted to the FDA by 30 April 2024; and the final protocol will be submitted to the FDA by 16 August 2024. Start of data collection is planned on 19 August 2024, pending FDA endorsement of the study protocol and SAP, and the end of data collection on 15 September 2025. The planned timeline includes three interim reports focusing on the analysis of the RSV seasons across two years, that are strategically scheduled: Interim report 1 will cover the 2023/2024 RSV season's SCRI and descriptive analysis (due to the FDA by 20 December 2024); Interim report 2 and Interim report 3 are due on 21 February 2025 and 08 August 2025, respectively, and will cover the RCA analyses in the 2024/2025 RSV season. The study concludes with a final report presenting the results of 2023/2024 and 2024/2025 RSV seasons' SCRI and descriptive analyses separately, as well as a pooled analysis for the SCRI and descriptive analysis findings from both seasons, to be submitted to the FDA by 30 January 2026.

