### 9.7.1. Data Lag

In the analysis of CMS Medicare data, the approach to account for data lags in the RCA and SCRI is to delay the analysis for at least 60 days to allow for at least 90% capture of data for post-vaccination follow-up period. Prior research suggests that ≥90% of IP and OP claims were submitted to the CMS within 2 months after service date. (14, 15) While imposing a lag in the analysis negatively impacts the timeliness of safety assessment, it allows the data to be more complete and thus increases the validity of results. In a non-pandemic setting where the initial uptake for the RSV vaccines is modest, the trade-off between timeliness and validity is deemed acceptable, and a similar approach has been used in prior safety monitoring for Shingrix after the vaccine approval.(27) Data lags will be assessed during the interim reports and a lag longer than 60 days (e.g., 90 days) may be considered for the final analysis, as necessary and feasible, to accrue the most stable data.

The PharMetrics Plus data has a data lag of approximately 6 months due to claims adjudication and completeness, making it unsuitable for the monthly sequential monitoring component (i.e., RCA) of the study. However, it will effectively contribute to the descriptive analysis (SCRI may be considered contingent on sufficient sample size), to be conducted towards the end of each RSV season and at the final two-season pooled analysis. This

analytic arrangement accounts for the data lag and still generates timely safety data for GBS in individuals aged 60-64 years following exposure to ABRYSVO.

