#### 9.9. Limitations of the Research Methods

This study uses a large real-world data (RWD) source of U.S. older adults, which is representative of the patient population of interest. However, use of claims databases has limitations, especially regarding potential misclassification of study variables. In this study, the primary outcome of interest, GBS, will be identified based on a validated claims-based algorithm using ICD-10 codes in inpatient Medicare data. To account for the possibility of outcome misclassification, PPV-adjusted bias analysis will be conducted to assess the robustness of results.

In addition, the CMS Medicare database has a delay, i.e., "claims lag", between when a service occurs and when the claim or encounter appears in the database. It was estimated that 91% of inpatient claims, 90% of outpatient, 96% of pharmacy claims and 87% of Carrier claims were estimated to be submitted within 2 months after service date.(14, 15) Therefore, to ensure at least 90% data completeness for this study, data are allowed to mature and complete for a minimum period of 2 months after the end of follow-up period. If there is no association between ABRYSVO and GBS, the 90% data completeness is likely to overestimate the risk of GBS by no more than 10%. The PharMetrics Plus database, which consists of fully adjudicated claims, has a lag of approximately 6 months due to claim adjudication and completion.

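### The data-collection end date of 15 September 2025 falls before the protocol's own PharMetrics maturation date and short of its stated six-month lag, so late-season GBS follow-up in ages 60-64 may be incomplete

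*Protocol*

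**What the plan says.** The protocol describes PharMetrics Plus as holding "fully-adjudicated claims with a data lag of approximately six months" (Section 9.1.3.1, note to Figure 6). Section 9.7.1 repeats this ("The PharMetrics Plus data has a data lag of approximately 6 months due to claims adjudication and completeness"), as does Section 9.9 ("has a lag of approximately 6 months due to claim adjudication and completion"), and Section 9.4.2 agrees. The Figure 6 note adds that "The indexing period for the descriptive analysis has accounted for the lag".

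Figure 6 gives a date chain for each season: end of indexing, end of the 42-day follow-up, end of a further 7 days for GBS capture, and complete maturation. For 2023/2024 the chain ends "29 Feb 2024 11 Apr 2024 18 Apr 2024 01 Sept 2024". For 2024/2025 and for both seasons combined, the corresponding dates are 28 February, 11 April, 18 April and 01 October 2025.

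The Abstract's milestones put "the end of data collection on 15 September 2025", and the table in Section 6 gives the same date. Neither place makes an exception for PharMetrics, and the protocol gives no separate PharMetrics extraction date. The final report, due 30 January 2026, presents both seasons separately and combined.

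**The concern.** Two statements in the current text cannot both be followed. If data collection closes on the milestone date, the 2024/2025 and combined PharMetrics analyses use data that Figure 6 itself treats as not yet mature. If the analysis waits for Figure 6's date, the milestone is missed. Separately, the 2023/2024 maturation date looks too early for the stated lag.

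PharMetrics is the only source for ages 60-64, and describing GBS incidence in that group is one of the three study objectives. The outcome needs an inpatient claim. If vaccination claims are mature but hospital claims for the last vaccinees are not, the incidence is too low. In a group where very few cases are expected, one missing case would change the description.

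**Working it through.** **Inputs.** End of indexing, end of follow-up, end of capture and maturation dates: Figure 6. End of data collection: Abstract and Section 6. Lag of approximately six months: Sections 9.1.3.1, 9.4.2, 9.7.1 and 9.9. Risk intervals of 1-21 days (primary) and 1-42 days (secondary): Section 9.1.3.1. Recipients and background rate: Section 9.5. Assumption: six months is taken as 183 days, and a month as 30.44 days.

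**Step 1: reproduce the first part of Figure 6.** 29 Feb 2024 + 42 days = 11 Apr 2024, and + 7 days = 18 Apr 2024. 28 Feb 2025 + 42 days = 11 Apr 2025, and + 7 days = 18 Apr 2025. These dates agree with the figure.

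**Step 2: time allowed for maturation, by starting point.**

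| Cut-off | from end of indexing | from end of follow-up | from end of capture |
|---|---|---|---|
| 01 Sept 2024 (Figure 6, 2023/2024) | 185 d (6.1 mo) | 143 d (4.7 mo) | 136 d (4.5 mo) |
| 01 Oct 2025 (Figure 6, 2024/2025 and combined) | 215 d (7.1 mo) | 173 d (5.7 mo) | 166 d (5.5 mo) |
| 15 Sept 2025 (end of data collection) | 199 d (6.5 mo) | 157 d (5.2 mo) | 150 d (4.9 mo) |

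- The milestone precedes Figure 6's 2025 date by 16 days.
- The 2023/2024 date reaches six months only if the lag is counted from the last vaccination. For Medicare, Section 9.9 counts maturation from the end of follow-up, which is the relevant starting point for an outcome.
- The same 42 + 7-day design is given 136 days in one season and 166 in the other, a difference of 30 days that is not explained.

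**Step 3: doses whose window is mature at a given cut.** Last fully mature dose = cut date − 183 − (interval length + 7).

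| Cut | services mature to | last mature dose, 21 + 7 d | doses after it | last mature dose, 42 + 7 d | doses after it |
|---|---|---|---|---|---|
| 15 Sept 2025 | 16 Mar 2025 | 16 Feb 2025 | last 12 days (17-28 Feb) | 26 Jan 2025 | last 33 days (27 Jan-28 Feb) |
| 01 Oct 2025 | 1 Apr 2025 | 4 Mar 2025 | none | 11 Feb 2025 | last 17 days (12-28 Feb) |

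**Step 4: direction.** At 15 September 2025 the youngest dose is 199 days old, so under the 183-day assumption all vaccination claims are mature. Hospital claims for services after 16 March 2025 are not. Any error would therefore lower the incidence. The protocol gives no completeness curve for PharMetrics, so the size cannot be derived.

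**Step 5: scale.** Expected background cases = recipients × days / 365.25 × rate. With 36,000 recipients (those with one year of enrolment, claims through 31 December 2023) and 4.6 per 100,000 person-years:

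- 21 days: 36,000 × 21/365.25 × 0.000046 = 0.095
- 42 days: 36,000 × 42/365.25 × 0.000046 = 0.19

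The rate is for Medicare beneficiaries aged 65 and over; applying it to ages 60-64 is an assumption. These figures cover the whole cohort, and the late doses account for only a part of them.

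**Step 6: six months from the proper starting points.** From the end of follow-up: 11 October 2024 and 11 October 2025. From the end of capture: 18 October 2024 and 18 October 2025.

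**The case against.** A reader might infer that late-season cases in ages 60-64 are in fact under-counted, and that the analyses cannot be run on mature data. The protocol does not show that. It gives no PharMetrics extraction date. Interim report 1, which carried the 2023/2024 results, was due 20 December 2024, 246 days (8.1 months) after capture closed, so a cut later than 01 September 2024 was possible. The 2023/2024 season is also reported again in the final report, and any 2025 extract would be well past six months for it.

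A reader might also call the Figure 6 note simply false, or treat 01 October 2025 as an error. Neither holds in full. The note speaks of the indexing period, and from the end of indexing both Figure 6 dates exceed six months. The lag is only approximate, and 5.5 to 5.7 months is a fair reading of it. At 01 October 2025 the primary 21-day interval is mature for every dose, even with the 7 capture days added.

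Finally, the analysis is descriptive, well under one background case is expected, and Section 9.9 already concedes that the ability to evaluate ages 60-64 will be limited.

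All of this stands, and it reduces the point to a possible shortfall of small absolute size. It does not remove the conflict between the milestone and Figure 6, and it does not make 4.5 months after capture match a lag of about six.

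**Conclusion.** The concern holds in a limited form. The end of data collection contradicts Figure 6 by 16 days and allows 4.9 months after capture against a stated lag of about six. Figure 6's 2023/2024 date is also short, at 4.5 months after capture, while its 2024/2025 date is roughly consistent with the lag. Keeping to the milestone may leave follow-up incomplete for about the last 12 days of 2024/2025 doses in the primary interval, or the last 33 days in the secondary one, and incidence in ages 60-64 may then be under-stated. Those day counts rest on reading the lag as 183 days and including the 7 capture days. The effect on counts is small and is unlikely to alter any inference. The reason to act is that the schedule cannot be followed as written and the note assures readers that the lag has been handled.

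**What to change.** - Set the PharMetrics data cut for the 2024/2025 and combined analyses no earlier than about six months after follow-up and capture end, that is, about mid-October 2025, and state that date.
- Move the end-of-data-collection milestone in the Abstract and Section 6 to match, or give PharMetrics its own milestone.
- Use the same refreshed extract for the 2023/2024 results in the final report, and say so.
- Correct Figure 6's 2023/2024 maturation date, and reword its note to say from which date the lag is counted.

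The cost is one later extraction and a short text correction. From 18 October 2025 to the final report on 30 January 2026 there are 104 days, so the report date need not move on this account.
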